1 INTRODUCTION

Type 2 diabetes is a national epidemic (1, 2) with significant macro and microvascular complications (3). Insulin resistance in pre-diabetes and overt diabetes are associated with endothelial dysfunction (4).

A few studies indicate that stem cells particularly EPCs can act as a suitable bio-marker (5-7, 9) for monitoring cardiovascular morbidity. In this proposal we suggest that EPCs or CD34 positive cells (defined as CD34/VEGFR2+ cells) can act as a suitable cellular biomarker for estimating and following endothelial dysfunction in early type 2 diabetes patients with CKD. EPCs have been shown to be dysfunctional in both CKD patients and type 2 DM patients. (5, 7, 31, 35)

Linagliptin (TRADJENTA) tablets are indicated as an adjunct to diet and exercise to improve glycemic control in adults with type 2 diabetes mellitus. No dose adjustment is recommended for patients with renal impairment. (29)

EPCs have been used as a regenerative tool in ischemic myocardium and diabetic wound healing (8, 10-13). Endothelial dysfunction with associated inflammation may be a consequence of excess intra-cellular super-oxide presence in a setting of diabetes which is a pro-oxidative stress condition ultimately leading to poor EPC function and senescence (14).

Though lifestyle modification has been proposed as a main stay for prevention and treatment of early type 2 diabetes, (2, 15-19) several new therapies for diabetes have been developed in recent years (2). Incretins and incretin mimetics appear to hold promise. Mechanism of positive effect of exercise and oral hypoglycemic agents can be very different. (44-50)

DPP-4 inhibitors have been shown to increase EPCs in patients with type 2 diabetes (20) reportedly via SDF-1 alpha up-regulation. Interestingly, up-regulation of SDF-1 alpha and vascular endothelial growth factor (VEGF), both chemotactic factors increase mobilization and recruitment of EPCs in the face of acute ischemic injury for repair and regeneration. (21-24).

Several studies have shown positive effect of incretins (Glucagon like peptide, GLP-1) and incretin receptor agonists (GLP-1 receptor agonists) on cardiovascular risk factors in type 2 diabetes patients (20, 25) and even in patients with chronic heart failure and left ventricular dysfunction who do not have diabetes (26, 27).

DPP-4 Inhibitors may have cardio-protective effects of their own, as they increase bio-availability of endogenous GLP-1. They improve blood flow and nitric oxide production in

endothelium (28, 29). These are unique properties not demonstrated by other oral diabetes medications (29). The mechanism underlying these effects may be mediated by increased nitric oxide bioavailability but is not completely known. However these beneficial effects appear to be independent of glycemia reduction.

It is however unknown whether Linagliptin will have any positive effect on human EPC function where two prominent cardiovascular risk factors co-exist such as CKD and type 2 diabetes.

Therefore we plan to investigate if Linagliptin can alter function and gene expression of CD34+ cells in a setting of CKD and type 2 diabetes. We choose to look at non geriatric adult population with early type 2 diabetes (≤ 15 years of duration) at an early phase of renal impairment (stages 1-3).

We specifically choose to exclude known CVD disease patients and early type 2 DM patients with early CKD as this cohort may be still retain capability to reverse or halt persistent endothelial damage seen in type 2 diabetes and CKD (3,30,35).

Our preliminary study results , which just finished, looked at effect of 150min/week of aerobic physical activity on EPCs in pre-diabetes population show that interventions even though non pharmaceutical can lead to quick (within 4 weeks) improvement in gene expression and function of CD34+ cells. These cellular changes are reproducible and consistent with other outcome measures such as serum biochemistry and vessel wall dilation measures such as flow mediated dilatation. (34)

Research Hypothesis:

We hypothesize that Linagliptin, a member of DPP-4 inhibitor group of drugs may be able to improve number and function of CD34+ endothelial progenitor cells by up-regulating chemotactic agent SDF1 alpha (DPP-4 degrades SDF-1) and its receptor CXCR4 (7, 20, 21) and thereby improving EPC migration and overall endothelial function. We also propose that this expected cardiovascular benefit is independent of HbA1C reduction. (30, 31)

In this proposed study we plan to recruit patients with type 2 diabetes of ≤ 15 years duration (in early phase of diagnosis), who are on a stable dose of insulin, Metformin, or both for at least 3 months either short or long acting but still remain inadequately controlled with HbA1C between 6.5% and 10% (both values inclusive), but not overtly out of control ($> 10\%$ of HbA1C).

The patient will adjust insulin levels so as to keep their HbA1C levels under 10.0%, for health measures. If the HbA1c rises above 10.0% then the PI will speak with the patient and provide a documented form indicating the insulin dose adjustment that should be

made. Initially life-style intervention with diet and regular aerobic activity (as per Standards of Diabetes Care: Diabetes Care Supplement: Jan 2014) along with insulin titration will be undertaken for initial 4 weeks (time between screening visit and 1st visit). Subjects will begin taking 5.0 mg of Linagliptin or placebo after initial 4 weeks. Subjects will be withdrawn from the study if the medication or placebo is not tolerated.

2 STUDY OBJECTIVES

2.1 Primary Objective

To investigate the effect of Linagliptin on Endothelial progenitor cells (CD34 positive cells) in patients whose HbA1C is between 6.5 to 10% (both inclusive) while being on treatment with a stable dose of insulin, Metformin, or both for the preceding 3 months before enrollment.

Cellular markers: We will use patient's peripheral blood derived CD34+ cells looking at number, function and gene expression changes pre and post Linagliptin over 12 weeks of therapy.

Urinary Function Marker in CKD: We will estimate 24hr urinary protein estimation and creatinine clearance (This is measured via the micro-albumin/Creatinine ratio provided from a random spot urine sample).

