
Study Objectives:
 
 • Primary: • Secondary: 	
The primary objective is to ascertain if addition of Linagliptin improves CD34+ cell function and gene expression in early type 2 diabetes patients with CKD stage 1-3, which will be correlated to improvement in 24hr urinary protein estimation and creatinine clearance (obtained via micro-albumin/creatinine ratio from a spot urine sample).
 
The secondary objective is to correlate the cellular outcome measures with other measures of endothelial function such as:
 
 1. Arterial stiffness measures with pulse wave analysis and pulse wave velocity measurements 2. Serum biochemistry looking at surrogates of endothelial health, endothelial inflammation, appetite controlling hormone levels and fasting glucose, insulin and lipid profile. 3. Resting Metabolic Rate measurement 
Study Outcome Measures
 
Primary:
 
To investigate the effect of Linagliptin on Endothelial function in patients inadequately controlled (HbA1C ≥ 6.5 % to ≤ 10%) while being treated with stable Insulin, Metformin, or both.
 
 • Cellular markers. We will study pre and post Linagliptin treatment changes in number, function and gene expression of patients' peripheral blood-derived CD34+ cells. • 24hr urinary protein estimation and creatinine clearance. 
Secondary:
 
 • To investigate the effect of Linagliptin treatment on serum endothelial inflammatory markers including high sensitivity C-reactive protein (hs-CRP), IL-6, TNF-alpha, and fasting lipid profile including ApoA1 and ApoB. 
Glycemic control will be evaluated by measuring fasting blood glucose, insulin, and HbA1c levels and assessing insulin resistance using HOMA-IR
 
 • Adiposity, measured using the Tanita Body Composition Analyzer scale, measured as percentage body fat. • Estimation of Creatinine clearance and Proteinuria estimation. • Vessel health will be assessed by systolic and diastolic blood pressure and Arterial stiffness assessed using vascular flow and wave measurement equipment, SphygmoCor CP system from ATCOR. • The sphygmocor system also allows us to estimate central and aortic blood pressure. • Resting Metabolic Rate (RMR, similar to Resting Energy expenditure measurement) at baseline, midway point (week 6) and post therapy.
--	---

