2.2 Secondary Objectives

To investigate the effect of Linagliptin treatment on serum endothelium inflammatory markers including: C-reactive protein (hs-CRP), IL-6, TNF-alpha, and fasting lipid profile including ApoA1 and ApoB (5, 6, 30, 36).

Glycemic control will be evaluated by measuring fasting blood glucose, insulin levels and HbA1c. Fasting blood glucose, insulin and lipid profile will be used to assess insulin resistance (32, 37)

Adiposity will be measured using the Tanita Body Composition Analyzer scale, measured as percentage body fat (33). Serum will be used to estimate levels of SDF1-Alpha, VEGF, and GLP1 levels by ELISA (25, 28, 29, and 30).

We also intend to follow resting Metabolic Rate at baseline, midway, and post DPP4 inhibitor therapy to ascertain if Linagliptin has any effect on RMR (56).

Kidney health will be monitored by creatinine clearance and microalbumin/ creatinine levels, which will be obtained from the spot urine sample.

- a. *Subjects will have the option of opting into a sub-study that is being where 10-20 mL of the excess fresh spot urine that has been collected will be used for exosome analysis. This is optional, and is not required of subjects. For details of urine-exosome study please see the appendix.*

[figure not shown]
The biochemical or bio-inflammatory markers are an important marker of endothelial inflammation and dysfunction along with glycemic markers and markers of arterial stiffness (36-43, 55, 57). Literature suggests that DPP4 inhibitors and GLP1 modifies and modulates hemopoietic stem cells and vaso dilatation (37, 44, 45).

Vessel health will be assessed by degree of arterial stiffness, using arterial tonometry. The central and the aortic pressure is assessed by pulse wave analysis (PWA) and pulse wave velocity (PWV) . Arterial stiffness will be assessed using vascular flow and wave form analysis equipment, SphygmoCor CP system from ATCOR. (56)

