3.2.1 Inclusion Criteria

1) Signed Written Informed Consent

- Before any study procedures are performed, subjects will have the details of the study described to them, and they will be given a written informed consent document to read. Then, if subjects consent to participate in the study, they will indicate that consent by signing and dating the informed consent document in the presence of study personnel.

2) Target Population

- Subjects with a diagnosis of Type 2 diabetes mellitus within the previous 15 years using criteria of the American Diabetes Association.

- Currently treated with Insulin (long or short acting or combination), Metformin (stable dose of 1-2 grams/day), or a stable dose of both.
- HbA1C between 6.5% and 10% (both inclusive)
- BMI 25-39.9 kg/m² both inclusive.
- History of Stage 1-3 CKD shown by a laboratory test taken within the past 2 years

CKD Staging:

Estimated Glomerular Filtration Rate Serum Cr should be used to estimate glomerular filtration rate (GFR). Estimated GFR (eGFR) is commonly reported by laboratories or can be estimated using formulae such as the Modification of Diet in Renal Disease (MDRD) study equation or the Chronic Kidney Disease Epidemiology Collaboration (CKD-EPI) equation. The latter is the preferred GFR estimating equation. GFR calculators are available at [http:// www.nkdep.nih.gov](http://www.nkdep.nih.gov).

Abnormal urinary albumin excretion and eGFR may be used to stage chronic kidney disease (CKD). The National Kidney Foundation classification (Table below) is based on **both kidney damage (UACR at or above 30 mg/g Cr) and eGFR.**

Normal UACR is defined as less than 30 mg/g Cr, and increased urinary albumin excretion is defined as at or above 30 mg/g Cr. Because of variability in urinary albumin excretion, ideally two (at least one) specimens of UACR should have been collected within a 3- to 6-month period before considering a patient to have albuminuria.

Stage -- Description -- GFR (mL/min/1.73 m²)

Stage 1 Kidney damage* with normal or increased GFR \geq 90

2 Kidney damage* with mildly decreased eGFR 60–89

3 Moderately decreased eGFR 30–59

4 Severely decreased eGFR 15–29

5 Kidney failure ,15 or dialysis

*Kidney damage is defined as abnormalities on pathological, urine, blood, or imaging tests.¹

3) Age and Reproductive Status

Men and women, 40 to 70 years of age.

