3.2.2 Exclusion Criteria

- Type 1 diabetes mellitus
- History of diabetic ketoacidosis or hyperosmolar non-ketotic coma
- Low hematocrit (< 28 Units)
- History of pancreatitis, or cancer (except basal cell carcinoma and cancer that is cured or not active or being treated in the past five years)
- Previous coronary event or history of cerebrovascular event within 6 months of screening or active or clinically significant coronary and/or peripheral vascular disease
- CKD Stages 4 and 5 (estimated CrCl < 30 mL/min)
- Beginning Statin medications or of change of Statin dose in the last 3 months,
- Use of oral or injectable anti-diabetic medication other than Insulin and Metformin. We did not want to bring in too many variables in the control arm and wanted to avoid a combination of insulin and other OHAs as the results might be difficult to interpret.
- Patients will be off other OHA (other than Metformin) before randomization and inclusion in the study.
- Use of consistent long-term steroid medication (oral, inhaled, injected) within the last 3 months
- Untreated Systolic BP > 140 mmHg and Diastolic BP > 90 mmHg
- Active wounds or recent surgery within 3 months
- Inflammatory disease, or current chronic use of anti-inflammatory drugs in the last 3 months.

- Untreated hyper/hypothyroidism
- Contraindications for moderate exercise
- Implanted devices (e.g., pacemakers) that may interact with Tanita scale

Physical and Laboratory Test Findings

- Pre-existing liver disease and/or ALT and AST >2.5X's UNL,
- serum creatinine levels ≥ 2.0 with estimated CrCl < 30 mL/min)
- Triglycerides >450 mg/dL

Allergies and Adverse Drug Reactions

- Subjects with a history of any serious hypersensitivity reaction to Linagliptin or another DPP-4 inhibitor.

Sex and Reproductive Status

- Women in reproductive age group will be included in the study but encouraged to use contraceptive method to avoid pregnancy within 16 weeks of study duration.
- Women who are pregnant or breast-feeding will be excluded.

Prohibited Treatments and/or Therapies

Treatment with a strong cytochrome P450 3A4 (CYP3A4) or P-gp inducer (i.e. rifampin)

Other Exclusion Criteria

- Prisoners or subjects who are involuntarily incarcerated.
- Subjects who are compulsorily detained for treatment of either a psychiatric or physical (e.g., infectious disease) illness.

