3.2.3 Discontinuation of Subjects from Treatment

Subjects MUST discontinue investigational product (and non-investigational product at the discretion of the investigator) for any of the following reasons:

- Withdrawal of informed consent (subject's decision to withdraw for any reason).
- Any clinical adverse event, laboratory abnormality, or inter-current illness which, in the opinion of the investigator, indicates that continued participation in the study is not in the best interest of the subject.

- Patients in CKD stages 1-3 who progress to stages 4 and beyond, post screening, will be excluded also.
- Concomitant treatment with a strong systemic cytochrome P450 3A4 (CYP 3A4) or P-gp inducer such as rifampicin. Use of alternative treatments to Linagliptin is recommended.
- Pregnancy
 - Pregnant patients will be advised to contact the investigator or study staff immediately if they suspect they might be pregnant (e.g., missed or late menstrual period) at any time during study participation.
- Loss of ability to freely provide consent through imprisonment or involuntary incarceration for treatment of either a psychiatric or physical (e.g., infectious disease) illness.
- If pancreatitis is suspected, promptly discontinue treatment with Linagliptin

All subjects who discontinue should comply with protocol-specified follow-up procedures outlined before. The only exception to this requirement is when a subject withdraws consent for all study procedures or loses the ability to consent freely (i.e., is imprisoned or involuntarily incarcerated for the treatment of either a psychiatric or physical illness). If a subject withdraws before completing the study, the reason for withdrawal must be documented appropriately.

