- Assessment of insulin sensitivity using the HOMA-IR (32), calculated from individual serum measures (fasting glucose (mg/dl)* insulin (μU/mL)/405) [37].
- Adiposity will be measured using the Tanita Body Composition Analyzer scale, measured as percentage body fat, BMI, waist-hip measurements (5, 55)
- Fasting lipid profile will be checked as a marker of insulin resistance and lipotoxicity at weeks 0, 6 and 12.
- We also intend to acquire Pulse wave analysis and Vascular Flow using SphygmoCor CP system from ATCOR to measure central arterial pressure and arterial stiffness (38-42). The secondary measures are indirect measures of endothelial inflammation in early type 2 diabetes patients. (30, 31, 55, 56, 57).
- Obtain indirect calorimetric measurements of basal metabolic rate using machine obtained from Korrs Medical. This is a non invasive procedure. We plan to measure the oxygen that the body consumes. It will help us calculate a patient's Resting Energy Expenditure (REE), commonly referred to as a Resting Metabolic Rate (RMR). As our protocol is directed to overweight and obese individuals using incretin therapy, it will be beneficial to note if the treatment modifies RMR. Description: The machine ReeVue by KORR directly measures the concentration of oxygen breathed out by each patient. The patient breathes through a simple mouthpiece as all the exhaled air is collected and analyzed. Because there is a direct correlation between oxygen consumed and calories burned (4.813 calories for every milliliter of oxygen consumed), an accurate measurement of oxygen consumption is an effective measurement of calorie consumption. The machine uses a one-way valve in the disposable (MetaBreather) mouthpiece. This draws in fresh room air with each inspiratory breath and eliminates concerns about cross contamination. The disposable mouthpiece is thrown away. It is unnecessary to clean the equipment or the tubing between each patient. This

equipment is FDA approved and has been used in physician offices as an oxygen uptake test with associated CPT code #94690. (58)

- Urine pregnancy testing for women of child bearing potential
- Creatinine Clearance and proteinuria estimation via random spot urine.

We will obtain a total of 85 mL of peripheral blood per visit. Of these 85 mL, 60 mL will be used to obtain CD34+ cells from MNC population and 25 mL for biochemistry and serum ELISA assays.

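### Creatinine clearance, listed under Primary, is to be taken from a random spot urine sample, which cannot yield a clearance

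*Combined protocol and SAP*

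**What the plan says.** Four places give urine as the source of creatinine clearance.

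- Section 2.1, Primary Objective: "creatinine clearance (This is measured via the micro-albumin/Creatinine ratio provided from a random spot urine sample".
- Protocol Synopsis, primary objective: "24hr urinary protein estimation and creatinine clearance (obtained via micro-albumin/creatinine ratio from a spot urine sample". The same pair of measures is then a bullet under Primary in the synopsis list of outcome measures.
- Section 2.2, Secondary Objectives: "Kidney health will be monitored by creatinine clearance and microalbumin/ creatinine levels, which will be obtained from the spot urine sample".
- Section 4.5, list of secondary measures: "Creatinine Clearance and proteinuria estimation via random spot urine".

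The synopsis also lists the measure under Secondary: "Estimation of Creatinine clearance and Proteinuria estimation". It therefore sits in two tiers.

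The Time and Events Schedule in section 4.5 has a spot urine sample at weeks -4, 0, 6 and 12 and no timed collection. Appendix A names the laboratory test on that urine as the microalbumin/creatinine ratio.

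Elsewhere the protocol ties renal function to serum creatinine. For CKD staging, section 3.2.1 states "Serum Cr should be used to estimate glomerular filtration rate (GFR" and prefers the CKD-EPI equation. Section 3.2.2 sets an exclusion limit of "serum creatinine levels ≥ 2.0 with estimated CrCl < 30 mL/min". Neither passage is linked to the clearance outcome.

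**The concern.** Clearance is a flow: the volume of plasma cleared of creatinine per minute. UACR compares two concentrations in one urine sample. The second does not determine the first, so the plan gives this Primary-listed outcome a source that cannot produce it.

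The title asks about improvement in renal failure, and the synopsis says the CD34+ results will be correlated with improvement in this measure. As written, albuminuria is the only renal quantity with a workable route. Two outcomes are then likely. Either a UACR is reported under the name of clearance, or a filtration formula is chosen after the data are in, which leaves a Primary-listed outcome defined post hoc. The mixed model in section 5 needs a defined numeric outcome, and for filtration there is none.

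The protein half has a milder fault. A spot UACR can serve as a rough index of daily albumin excretion, but it is not a 24-hour total protein. Total urinary protein is named as an assay only in the optional exosome study in Appendix A.

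**Working it through.** The plan states no figure on this point, so there is nothing to reproduce. The check is whether the stated source contains the quantities that the outcome needs.

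**Definitions**

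- CrCl = (urine creatinine × urine volume) / (serum creatinine × collection time). With daily creatinine excretion in mg/day and serum creatinine in mg/dL: CrCl (mL/min) = excretion / (serum creatinine × 1440) × 100.
- UACR (mg/g) = albumin excretion (mg/day) / creatinine excretion (g/day), or equally urine albumin / urine creatinine in the same sample.

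A spot sample supplies urine albumin and urine creatinine. It does not supply volume per unit time or serum creatinine. All inputs below are illustrative assumptions, because the documents give none.

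**Check 1: serum creatinine changes within a patient.** Steady state, albumin excretion 120 mg/day. First row: 1200 / (1.0 × 1440) × 100 = 83.3 mL/min, and 120 / 1.2 = 100 mg/g.

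| Creatinine excretion (mg/day) | CrCl at serum 1.0 mg/dL | at 1.25 | at 1.5 | UACR (mg/g) |
|---|---|---|---|---|
| 1200 | 83.3 | 66.7 | 55.6 | 100 throughout |
| 800 | 55.6 | 44.4 | 37.0 | 150 throughout |
| 2000 | 138.9 | 111.1 | 92.6 | 60 throughout |

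In every row clearance falls by 20% (1 − 1/1.25) and then by 33% (1 − 1/1.5). UACR does not move, because serum creatinine is not in its formula.

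**Check 2: one fixed spot sample.** Urine albumin 100 mg/L and urine creatinine 100 mg/dL give UACR 100 mg/g.

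- 1000 mL/day, serum creatinine 2.0 mg/dL: 100 × 1000 / (2.0 × 1440) = 34.7 mL/min.
- 2000 mL/day, serum creatinine 0.8 mg/dL: 100 × 2000 / (0.8 × 1440) = 173.6 mL/min.

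The same urine result fits both.

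**Check 3: clearance fixed.** At 1500 mL/day and serum creatinine 1.2 mg/dL, CrCl = 100 × 1500 / (1.2 × 1440) = 86.8 mL/min. Varying urine albumin alone from 10 to 1000 mg/L moves UACR from 10 to 1000 mg/g with clearance unchanged.

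Neither quantity determines the other.

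**The case against.** The strongest reply is that the wording is loose rather than impossible. In section 2.1 and the synopsis the parenthesis follows a pair of measures and could describe only the protein estimate. The qualifiers in sections 2.2 and 4.5 could likewise attach only to the albumin or protein term. This is grammatically possible, but it needs the less natural reading in all four places. Even then clearance would have no stated method.

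The second reply is that filtration may well be followed. Biochemistry is drawn at weeks 0, 6 and 12. Appendix A mentions a GFR calculation. Section 3.2.3 acts on a change of CKD stage: "Patients in CKD stages 1-3 who progress to stages 4 and beyond, post screening, will be excluded also". This stands in part: a serum-based estimate may be what was intended, and the data may exist. But the panel is not itemised, and no section designates a serum-creatinine-based outcome at those visits.

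Third, the example uses assumed inputs and holds excretion constant, so UACR is unchanged by construction. That is true. It shows that a variable is missing from the stated source. It estimates no bias or loss of power in this trial.

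Fourth, the study calls itself a pilot, and its sample size rests on CD34+/KDR+ cells and VEGF. This limits the reach of the point, but the measure is still listed under Primary.

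Last, eGFR is not creatinine clearance, and a timed collection with paired serum creatinine would also be valid. That is also true. The case for eGFR is that it fits the visits as scheduled.

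**Conclusion.** The concern holds. The stated method cannot give creatinine clearance, and the trial has no defined filtration measure to analyse or to correlate with the cell results. This follows from the definitions and does not depend on the illustrative values. With those values, a 20% or 33% fall in clearance leaves UACR unchanged.

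The reach is one outcome listed under Primary, at weeks 0, 6 and 12, and the planned correlation with it. The CD34+ outcomes and the power calculation stand apart from this point. Whether serum creatinine is already in the biochemistry panel is not stated, so the outcome may be recoverable once it is properly defined. It must be corrected, and before data lock, so that the definition does not depend on the results.

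**What to change.** Replace the combined protein and clearance outcome with two separately named measures at weeks 0, 6 and 12:

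1. Spot UACR, labelled as albuminuria and not as 24-hour protein.
2. eGFR by CKD-EPI, the equation that section 3.2.1 already prefers, from serum creatinine measured at the same visits.

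Then:

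- Remove the statement that clearance comes from spot urine in the synopsis, sections 2.1 and 2.2, and the measures list in section 4.5.
- Put each measure in one tier only.
- Name in the synopsis which of the two will be correlated with the CD34+ results.
- Confirm that serum creatinine is in the biochemistry panel, or add it.

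The cost is wording plus at most one serum assay on blood already drawn, with no new visit or timed urine collection. If the investigators want measured creatinine clearance itself, they would have to add a timed collection with paired serum creatinine, which costs more.
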